### **Anterior Chamber OCT**

Glaucoma in children is generally evaluated by measuring the intraocular pressure and assessing the cup-to-disc ratio of the optic disc. Gonioscopy, which is the “gold standard” in the evaluation of anterior chamber angles (Sharma R, 2013), is difficult to perform in children. Ultrasound biomicroscopy is another modality that has been used in children to assess the anterior segment of the eye. It uses ultrasound to image the anterior segment and studies have shown it to be consistent with gonioscopy. Its major disadvantage is that it requires an immersion shell to be placed on the eye which is generally not tolerated by young children. Due to its noninvasive nature, OCT may be useful for assessing the anterior segment of children after cataract surgery to evaluate risk factors for glaucoma as it is comparable to gonioscopy.

### **Nerve Fiber Layer OCT**

Spectral domain optical coherence tomography (SD-OCT) has been shown to be a powerful tool evaluating and managing adults with glaucoma, and can even predict among glaucoma suspect those eyes at higher risk for developing visual field loss (Mwanza et al., 2011; Miki et al., 2014). In children, peripapillary retinal nerve fiber layer thickness (RNFL) assessed by either time domain OCT [Hess et al; Nadeau et al., 2010] or, more recently, by SD-OCT [Alasil et al., 2013], has been shown to be effective in differentiating between normal eyes and eyes with glaucoma (Ghasia et al., 2013; Srinivasan et al., 2014). RNFL measurements of both eyes will be taken using the Heidelberg Spectralis OCT by a trained OCT imager. Average RNFL will be compared between the surgical and the normal fellow eyes for all subjects. Average RNFL will be compared among study eyes with glaucoma suspect or glaucoma status, and those without a glaucoma-related adverse event. Quadrant level analysis of RNFL thickness will be carried out to detect trend in thinning among those with glaucoma-related adverse events compared to normal fellow and unaffected study eyes. Similarly, the difference in average RNFL between study and control fellow eyes will be compared for children with glaucoma suspect, glaucoma, and those with neither. Average RNFL will be correlated with optic nerve head cupping and the presence or absence of glaucomatous optic neuropathy (assessed by masked review of stereophotographs) across all study eyes.

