### Phase 3 Definition and Diagnosis of Glaucoma:

In Phases 1 and 2, an eye was defined as having glaucoma if the following criteria were present: IOP >21 mmHg with one or more of the following anatomical changes: 1) corneal enlargement; 2) asymmetrical progressive myopic shift coupled with enlargement of the corneal diameter and/or axial length; 3) increased optic nerve cupping defined as an increase of  $\geq 0.2$  in the cup-to-disc ratio, or 4) the use of a surgical procedure for IOP control. An eye was defined as glaucoma suspect if any of the following criteria were present: 1) two consecutive IOP measurements >21 mmHg on different dates after topical corticosteroids had been discontinued without any of the anatomical changes listed above; or 2) glaucoma medications were used to control IOP without any of the anatomical changes listed above.

In Phase 3, an eye will be defined as having glaucoma if the following criteria are present: 1) IOP > 21mmHg; and 2) a progressive increase in cup-disc ratio, cup-disc asymmetry of  $\geq 0.2$ , or focal rim thinning. An eye will be defined as glaucoma suspect if any of the following criteria are present: 1) IOP > 21mmHg; or 2) glaucoma medications are being used to control IOP; or 3) an optic disc suspicious for glaucoma (e.g. increased cup-disc ratio). The criteria which will be used to diagnose glaucoma in Phase 3 will be the same as the criteria used in Phases 1 and 2 of the IATS, with the exception of ocular enlargement criteria. Unlike infants, children aged 5-10 years do not usually exhibit signs of ocular enlargement with elevated IOP. The criteria which will be used to diagnose glaucoma suspect in Phase 3 will also be the same as the criteria used in Phases 1 and 2 of the IATS with the exception that two consecutive IOP measurements >21 mmHg at two different visits will not be included in the definition since children in Phase 3 will only be examined once. In addition, since optic disc photographs will be taken at the 10Y exam, we have added a suspicious optic disc as another criterion for Phase 3. Since some children may be diagnosed as having glaucoma or glaucoma suspect between the five and 10 year evaluations, a review of medical records will be performed for all patients to determine who are classified as glaucoma or glaucoma suspect for Phase 3. This will assist in establishing diagnostic criteria and the age of onset for study purposes.

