### **Optic Nerve Fiber Layer OCT**

Spectral domain optical coherence tomography (SD-OCT) has been shown to be a powerful tool evaluating and managing adults with glaucoma, and can even predict among glaucoma suspect those eyes at higher risk for developing visual field loss (Mwanza et al., 2011; Miki et al, 2014). In children, peripapillary retinal nerve fiber layer thickness (RNFL) assessed by either time domain OCT [Hess et al; Nadeau et al., 2010] or, more recently, by SD-OCT [Alasil et al, 2013], has been shown to be effective in differentiating between normal eyes and eyes with glaucoma (Ghasia et al., 2013; Srinivasan et al, 2014). RNFL measurements of both eyes will be taken using the Heidelberg Spectralis OCT by a trained OCT imager, with a baseline signal strength of at least 25. Average RNFL will be compared between the surgical and the normal fellow eyes for all subjects, the latter serving as the control group. Average RNFL will be compared among study eyes with glaucoma suspect or glaucoma status, and those without a glaucoma-related adverse event. Quadrant level analysis of RNFL thickness will be carried out to detect trend in thinning among those with glaucoma-related adverse events compared to normal fellow and unaffected study eyes. Similarly, the difference in average RNFL between study and control fellow eyes will be compared for children with glaucoma suspect, glaucoma, and those with neither. Average RNFL will be correlated with optic nerve head cupping and the presence or absence of glaucomatous optic neuropathy (assessed by masked review of stereophotographs) across all study eyes.

The OCT data will be submitted digitally so that they can be reviewed remotely without copy/fax/scan issues. Evaluation will consist of a look at the mean NFL, the superior/inferior/nasal/temporal quadrant numbers, and symmetry with the fellow eye.

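### The quadrant RNFL analysis names unoperated fellow eyes as one reference for glaucomatous thinning and does not get the within-child contrast by glaucoma status that is planned for average RNFL

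*Combined protocol and SAP*

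**What the plan says.** Chapter 1 (Nerve Fiber Layer OCT) and Chapter 4 (Optic Nerve Fiber Layer OCT) give the same set of comparisons.

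- **Average RNFL, operated against fellow:** "Average RNFL will be compared between the surgical and the normal fellow eyes for all subjects, the latter serving as the control group" (Chapter 4 wording).
- **Average RNFL, operated against operated:** "Average RNFL will be compared among study eyes with glaucoma suspect or glaucoma status, and those without a glaucoma-related adverse event".
- **Average RNFL, within child by status:** "the difference in average RNFL between study and control fellow eyes will be compared for children with glaucoma suspect, glaucoma, and those with neither".
- **Quadrant RNFL:** one sentence, whose purpose is "to detect trend in thinning among those with glaucoma-related adverse events compared to normal fellow and unaffected study eyes".

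The quadrant sentence does not say whether the two references are used separately or combined, which one carries the conclusion, or how the two eyes of a child are handled. Statistical Analysis in Chapter 5 adds no RNFL method. The Inclusion Enrollment Report states that every child had a unilateral cataract and a normal fellow eye, so all fellow eyes are unoperated.

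**The concern.** A study eye differs from its fellow eye in more than glaucoma. It has had surgery, it is aphakic or pseudophakic, and its growth was hard to predict: pseudophakic eyes at age 5 ranged from -19.00 to +5.00 D (Myopic Shift and Accuracy of IOL Calculations). If any of this shifts the OCT reading, affected study eyes will differ from fellow eyes without any glaucoma effect. The fellow-eye contrast cannot tell the two apart, and a pooled reference only dilutes the problem.

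At stake is a statement that glaucoma thins particular quadrants when the data show only that operated eyes read differently. If operated eyes read thicker, the same contrast would hide real thinning.

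Pooling also breaks the error structure. Each unaffected child would supply two correlated comparator eyes, and each affected child would have one eye on each side of the comparison.

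**Working it through.** The plan states no effect size, power or sample size for any RNFL analysis, so there is no figure to reproduce. The check asks how much of a pure operated-eye offset enters each contrast when glaucoma has no effect.

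**Inputs from the documents**
- 114 children (Inclusion Enrollment Report), 57 of them randomized to CL (Study Design), so 114 - 57 = 57 to IOL.
- Glaucoma or suspect at 5 years: CL 35%, IOL 28% (Chapter 5, Glaucoma). 0.35 × 57 ≈ 20 and 0.28 × 57 ≈ 16, giving 36 affected and 114 - 36 = 78 unaffected.

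**Assumed, because the documents do not give them**
- Operated eyes read thinner by an offset d of 0 to 1 SD, the same in affected and unaffected study eyes.
- Inter-eye correlation ρ of 0.3 to 0.8.
- Two-sided 5% tests, and usable scans of both eyes in all children.

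**Step 1: share of the offset in each contrast.** Affected study eyes average μ - d. A reference made of F fellow eyes and U unaffected study eyes averages μ - d·U/(F + U). The apparent thinning is therefore d·F/(F + U).

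| Reference | F | U | Share of d read as thinning |
|---|---|---|---|
| Fellow eyes only | any | 0 | 100% |
| All fellow eyes pooled with unaffected study eyes | 114 | 78 | 114/192 = 59% |
| Affected children's fellow eyes pooled with unaffected study eyes | 36 | 78 | 36/114 = 32% |
| Unaffected study eyes only | 0 | 78 | 0% |
| Study-minus-fellow difference, affected against unaffected | – | – | (-d) - (-d) = 0 |

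The number affected may rise by age 10. With an assumed 45 affected and 69 unaffected, the second row becomes 114/183 = 62%.

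**Step 2: how often this would be declared thinning.** Simulation with 36 and 78 children, no glaucoma effect and 4,000 datasets per setting. The paired t-test was used for own fellow eyes and two-sample t-tests elsewhere. Ranges run over ρ = 0.3, 0.6 and 0.8.

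| Contrast | d = 0 | d = 0.25 SD | d = 0.5 SD | d = 1 SD |
|---|---|---|---|---|
| Affected against own fellow eyes | 4.8–5.1% | 23–64% | 68–99.5% | 99.9–100% |
| Pooled with all fellow eyes | 3.2–4.4% | 10–12% | 34–35% | 87–88% |
| Pooled with affected children's fellow eyes | 1.5–3.4% | 3–4% | 7–10% | 28–34% |
| Affected against unaffected study eyes | 4.8–5.4% | 4–6% | about 5% | 4–5% |
| Study-minus-fellow difference by status | 4.7–5.1% | 4–5% | about 5% | 4–5% |

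In the first row the test is right that operated and fellow eyes differ. It is wrong only if read as a glaucoma result. At d = 0 the pooled tests reject too rarely, because they ignore pairing.

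**Step 3: precision of the two contrasts that carry no offset.** In SD units, the standard error for affected against unaffected study eyes is √(1/36 + 1/78) = 0.201. For the difference by status it is this times √(2(1 - ρ)):
- ρ = 0.3: 0.201 × 1.183 = 0.238
- ρ = 0.5: 0.201 × 1.000 = 0.201
- ρ = 0.7: 0.201 × 0.775 = 0.156

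The within-child difference is the more precise only when ρ exceeds 0.5.

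**The case against.** A reader might infer that any operated-eye difference will be read as glaucomatous thinning. The documents do not support that. The same sentence names unaffected study eyes, which are operated, and a common offset cannot bias that contrast. Read as two comparisons, the sentence even allows an operation effect to be separated from a glaucoma effect. Nothing in the plan says the references are pooled or that eyes are treated as independent.

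A reader might also take the false-positive rates as predictions. They are not: the documents do not say that operated eyes read thinner, by how much, or in which direction.

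Three further points stand.
- Quadrants and average RNFL differ less than they first appear to. The average also gets a raw operated-against-fellow comparison, and Chapter 4 has quadrant values and symmetry with the fellow eye reviewed, though not as a test by glaucoma status.
- The within-child difference is not free of confounding. At age 5, IOL-group eyes with glaucoma had a median of -7.25 D against -1.69 D without, and no RNFL analysis is said to adjust for axial length.
- Selection on disc appearance is a separate matter. For suspect status the plan says "we have added a suspicious optic disc as another criterion for Phase 3", and the photographs are graded mainly by comparing study eye with fellow eye. This affects average RNFL and the within-child contrast as well.

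What the objection does not answer is that the plan leaves open which reference carries the conclusion, and one of the two cannot carry it.

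**Conclusion.** The point holds in limited form. Of the two quadrant references, the fellow-eye one carries 100% of any operated-eye offset, and pooling with all fellow eyes carries 59% at the 5-year counts. Unaffected study eyes carry none. The plan does not choose between them and does not extend to quadrants the contrast by status that it already specifies for average RNFL.

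The shares in Step 1 need only the counts and an offset common to all operated eyes. The error rates in Step 2 also rest on the assumed offset and correlation, and are illustrations. RNFL appears in none of the three Study Aims and in neither the primary nor the secondary glaucoma analysis of Chapter 5, so no comparison of IOL with CL depends on this. It is worth changing because the remedy is nearly free.

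**What to change.** In both RNFL sections, state for the quadrants that:

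1. The two references are analysed separately and not pooled.
2. Conclusions about glaucomatous thinning rest on affected against unaffected study eyes with the child's fellow eye as within-child control. That is the study-minus-fellow difference compared across glaucoma, suspect and neither, in a mixed model with child as random effect and a status-by-eye-by-quadrant term.
3. Raw comparisons with fellow eyes are descriptive. The same label suits the raw operated-against-fellow comparison of average RNFL.

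**Cost.** Some wording and slightly more analysis. Both eyes are already scanned and quadrant values already reviewed. Fitting the model to both eyes' values, rather than to computed differences, keeps children with only one gradable scan. If the inter-eye correlation is below 0.5, the difference is less precise than the plain study-eye contrast, so that contrast should be shown beside it.

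**What it does not cure.** Axial-length differences between affected and unaffected study eyes, and selection on disc appearance. A table splitting affected eyes by route to status (IOP or medication only, against disc appearance) would show the second.

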### **Myopic Shift and Accuracy of IOL Calculations**

[figure not shown]
During childhood, the human eye elongates and the cornea and the crystalline lens flatten. When the biometrics of the growing eye are perfectly calibrated, the eye remains emmetropic. However, if the crystalline lens is removed surgically, the corneal flattening that occurs in early childhood cannot offset the 3-4 mm of axial elongation that occurs during the first year of life and the additional axial elongation that occurs in some eyes even into the teenage years.(Gordon et al., 1985) While small myopic shifts after IOL implantation can be corrected with contact lenses or spectacles, large myopic shifts may require an IOL exchange.(Dahan et al., 1990) In children with unilateral pseudophakia, a large myopic shift may contribute to the development of anisometropic amblyopia and impaired binocularity. Most clinicians undercorrect infants after cataract surgery and IOL implantation in anticipation of a myopic shift.(BenEzra, 1996; Dahan, 1997; Thouvenin et al., 2003; Autrata, 2005; Gouws et al., 2006) However, there is no agreement regarding the optimal magnitude of this undercorrection. While small cases series have reported a mean myopic shift ranging from 5 to 7 D after IOL implantation during infancy, these studies are retrospective with variable lengths of follow-up.(McClatchey et al., 2000; Ashworth et al., 2007; Astle et al., 2007) In addition, co-morbidities

such as glaucoma and microphthalmos which may impact the magnitude of the myopic shift were not always exclusion criteria in these studies.

In the IATS, all pseudophakic eyes had a targeted undercorrection of 6 or 8 D at the time of cataract surgery and primary IOL implantation (age 4-6 weeks, 8 D; age 7-28 weeks, 6 D). Postoperatively, follow-up clinical examinations were performed by an IATS certified investigator at 1 day, 1 week, 3 months and then at 3 months  $\pm$  2 weeks intervals until age 4 years and then at ages 4.25, 4.5 and 5 years. The age 5 year examination, included a cycloplegic refraction to assess the refractive error in both the treated and untreated eyes. The median (25th, 75th percentiles) refractive error in the treated eyes in the IOL group was -2.25 D (-7.25, 0.00) (range, -19.00 to +5.00 D). As expected, the median refractive error was larger in with glaucoma (-7.25 D) compared to eyes without glaucoma (-1.69 D).

	# Patients	Median	IQR*	Range
Without Glaucoma	44	-1.69	-5.03 to 1.16	-18.00 to 5.00
With Glaucoma	11	-7.25	-16.50 to -3.50	-19.00 to -1.50

## **CHAPTER 2 RESEARCH DESIGN and METHODS**

The 114 patients enrolled in IATS will be examined within the year after their 10th birthday. A comprehensive ocular examination will be performed including tonometry and refractometry as well as measurements of central corneal thickness, keratometry, and axial length. Nerve fiber layer Optical Coherence Tomography (OCT) will also be performed. All data will be entered on standardized electronic Case Report Forms. All key personnel will maintain or acquire IATS certification according to the procedure described in the Manual of Procedures.

### **Informed Consent and Assent**

At the 5Y visit, all caregivers were asked to give written permission for the study staff to maintain contact after the closeout visit. If the parents(s) or legal guardian(s) have agreed to have their child return for a study visit at age 10 years, the study will be discussed with them and with the child. Written informed consent must be obtained from the parent(s) or legal guardian(s) of the child before performing any procedures that are not part of the patient's routine care. In addition, because these children are now old enough to assent to their medical treatment, they must give verbal assent or sign an approved Assent Form. If the child has been followed by a non-study ophthalmologist since the 5y visit, the caregiver will be asked to sign a Medical Records Release form in order to capture the interim history.

The accompanying Caregiver will be asked to fill out a brief form regarding the child's use of optical correction, occlusion therapy, or special education services.

### **Retention**

Attrition poses a significant threat to the internal validity of the proposed study given that attrition has been associated with low socioeconomic status and poor treatment adherence in chronic pediatric illnesses. The study group has been very successful in follow-up of the cohort and has experienced a very low attrition rate in both Phases 1 and 2 of the IATS. Nearly 90% of the mandated study visits were completed and more importantly, 100% of the Primary Outcome visits at age 12 months and 99% at age 4½ years were completed. All but 6 parents have signed a Permission to Contact Form allowing the Data Coordinating Center (DCC) to maintain contact with the participants and their parents even after they have completed the 5Y visit in Phase 2 of the study. Until mid 2015 the DCC will be maintaining contact with participants and their families in a variety of ways including: quarterly newsletters informing the families about key findings of the Study as well as providing information regarding visual development and ocular health, the popular IATS calendar, birthday cards, and periodic telephone contact with the families by the Site Coordinators. The DCC works to ensure that we have and maintain accurate addresses of the families, as well as contact information for other key individuals in each family's life. The Sites will begin trying to schedule the 10-year visit about 6 months in advance to ensure that there is adequate time to find any participants who may have moved and for whom there is not current address information available. In this case, the Clinical Coordinating Center and the Sites will collaborate to locate and retain these participants using available resources such as the family contacts and electronic search databases.

We will supplement our previously successful outreach programs using social media. Social media will provide us with another opportunity to engage participants and other interested stakeholders, and to inform these individuals about the Study's progress. Additionally, engaging participants has been an important component of our success in retaining participants.

Recent data suggest that 90% of Americans age 18 to 39 use the internet and 73% use social media, and that usage does not differ by race or ethnicity (<http://www.pewinternet.org/2013/12/30/social-media-update-2013>). The goal of including a social media presence in the IATS is to increase engagement with the Study and to enhance the sense of community among participants that was initiated through adherence phone calls, newsletters and calendars. We are adding this component to the proposed follow-up because of its increasing importance in American culture and because we will no longer be conducting adherence phone calls. Social media will be used by IATS as a mechanism of engaging participants and creating a sense of community for these families, and not as a method to collect data or personally identifiable data. However, we will use social media to request that participants contact to Study to ensure that we have accurate contact information.

Because of recent trends in social media, as noted above, IATS will focus its social media presence on Facebook, Twitter and Pinterest which have high penetration among women aged 30 to 49. To ensure that these sites are used and serve the goals of the study, we will ensure that postings are updated at least three times each week. The postings will provide updates to the Study's progress, updates on publications related to the study, information of interest to parents with school-aged children and information of interest to caregivers of children with cataracts and other eye conditions which are prevalent among this population. All posts will be reviewed by the Executive Committee prior to posting to ensure that the most relevant and accurate information is presented. Additionally, best practices and guidelines developed by Federal agencies (i.e., CDC and NIH) will be used to govern the implementation of social media in IATS.

To encourage participation in the study, the following steps will be taken: 1) families will be reimbursed for the time they invest in the study visit with monetary incentives (\$250 for attending the scheduled study visit and a \$50 gift card for the child), 2) travel costs will be reimbursed if it is a financial hardship for families to return for the study visit, and 3) families will receive IATS newsletters three times a year and an "IATS Kids" holiday calendar annually.

